2. Demonstrate modulation of neurophysiological aftereffects of PPC stimulation by manipulating behavioral state. Based on preliminary data, our working hypothesis is that motor excitability will increase after PPC stimulation and will increase even more after stimulation during grasp performance.
3. Assess the relationship between brain connectivity, plasticity and behavior in response to the behavioral state during brain stimulation. Our working hypothesis is that constraining the behavioral state during PPC stimulation will induce greater changes in functionally specific parietal-motor pathways within the targeted cortical grasping network, as compared to PPC stimulation alone. Exploratory analyses will examine correlations between changes in action performance, plasticity, and functional connectivity.

RESEARCH DESIGN:

Participants will be asked to participate in up to nine sessions – the sessions will take place in either the TMS laboratory in the Kinesiology Building ([name]) or the Functional MRI Laboratory located in the Bonisteel building ([name]). The visit schedule is as follows:

- Session 1: Screening + behavioral & neurophysiological measures (~2 hours)
- Session 2: fMRI (~1 hour)
- Session 3: TMS (~30 min)
- Session 4: TMS (~30 min)
- Session 5: TMS (~30 min)
- Session 6: TMS + behavioral & neurophysiological measures (~3 hours)
- Session 7: TMS + fMRI (~1 hour)
- Session 8*: fMRI (~1 hour)
- Session 9*: behavioral & neurophysiological measures (~1 hours)

*Option to complete visits 8 and 9 on the same day

Subjects will be randomly assigned to one of three rTMS intervention groups in a 1:1:1 ratio. As depicted in **Figure 1**, subjects will complete fMRI scans, electrophysiological measures with TMS, and behavioral measures before and after five consecutive rTMS sessions. The first fMRI assessment session on visit 2, without rTMS, will obtain baseline measurements of hand motor function, electrophysiology with TMS, and fMRI-derived connectivity (providing the PPC target

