We will determine an individualized left PPC stimulation location based on peak functional connectivity with the left motor cortex seed obtained at the baseline assessment on visit 1 using functional neuroimaging. This will account for individual variability in recruitment of the cortical grasping network and maximize the reliability of the rTMS-induced modulation. We will use those coordinates as the site of stimulation for the PPC target. The stimulation targets will be transformed from MNI space into each subject's original MRI space for anatomically guided TMS. We then will use a robust dual-site TMS 'hunting' procedure, recently developed by my laboratory, to determine the optimal PPC scalp location where TMS can effectively exert a grasp-specific facilitation of motor cortex on an object-driven grasp task inspired by previous work from both our group^{13,14,15} and others.^{16,17,18,19,20} For the vertex (control) target, we will locate the vertex according to the standard 10-20 system. We then will confirm using individualized fMRI from the baseline assessment session that the underlying cortical site is outside the functionally defined regions of interest for the targeted cortical grasp network, and adjust the coil on the scalp accordingly. We will use neuronavigation to enable reproducible placement of the TMS coil over the cortical targets for the multiple rTMS sessions. For the PPC stimulation alone intervention group, subjects will be instructed to maintain gaze on a fixation LED during stimulation. For vertex and PPC stimulation augmented with a task sessions, subjects will perform an object-driven grasping task.^{13,14,16,,21-26} Subjects will maintain fixation on a central LED in the midline (preview phase) for ~ 2 s. The illumination of an LED (green or red) then will instruct the subject to plan a precision grip towards either a small or large target object positioned in front of them. After 1 s, the LED will extinguish and cue subjects to execute the intended object-directed hand action. The presentation of the visual stimuli will be synchronized with the iTBS stimulation, which will occur 800 ms before the onset of every 'GO' cue in order to modulate cortical activity during both the planning and execution phase of the action.

Detailed objectives:

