The third aim of this study is to assess the relationship between brain connectivity, plasticity and behavior in response to the behavioral state during brain stimulation. Exploratory analyses will test for correlations between the three measures, to provide a richer picture of iTBS effects. In order to assess functional connectivity between disparate brain regions, we will calculate correlations between the time series of disparate brain regions. For each seeded region of interest, we will produce a whole brain map of Pearson's r values that can subsequently be transformed using Fisher's r-to-z transform to allow for standard statistical testing. Regions that display a high degree of correlation ($p < 0.05$, corrected for multiple comparisons) are assumed to be "functionally connected" with that node. To examine the effect of iTBS on functional connectivity, we will directly contrast the MRI sessions following iTBS PPC + Grasp with iTBS PPC alone and iTBS Vertex + Grasp using our previous methods.³⁵ Exploratory analyses will search for regions outside the a priori defined network that change

with stimulation to develop a comprehensive picture of how iTBS interacts with brain networks. All data from our fMRI scans also will be publicly posted at Open fMRI (<http://openfmri.org/>) to allow other researchers to validate our results and perform supplemental analyses.

MEASUREMENTS

The neurophysiological measurements for the current study are:

- **Motor threshold** in hand muscles as defined as the lowest TMS intensity needed to generate MEPs of >50 μ V in at least 5 of 10 trials when the muscle is completely relaxed (resting MT; RMT) and the minimum intensity required to produce MEPs of $\geq 200\mu$ V in at least 5 of 10 trials while the participant maintains 20% maximum contraction in the targeted hand muscle (active MT; AMT).
- **MEP amplitude** will be measured with 1 mV TMS intensity. A fixed stimulation intensity to elicit a ~ 1 mV MEP will be determined for each participant before testing to examine the changes in MEP after the different plasticity induction protocols. Twenty-four MEPs will be acquired at each time point. Stimuli will be applied every 5 s.

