- **Object directed grasping:** Subjects will perform a precision grip with the right hand towards either a small or large target object positioned in front of them. The illumination of an LED (green or red) will instruct the subject to plan a precision grip towards either a small or large target object positioned in front of them. After ~1 second, the LED will extinguish and cue subjects to execute the intended object-directed hand action. The presentation of the visual stimuli will be synchronized with the iTBS stimulation, which will occur 800ms before the onset of every "GO" cue in order to modulate cortical activity during both the planning and execution phase of the action.

Outcome measures for the current study are:

Primary Outcome Measures:

1. Percentage change in the time to complete the nine-hole peg test (9-HPT) to immediate post-intervention. 9-hole peg test is a manual dexterity measure, estimated as the time required to complete the task (seconds). Time Frame: Baseline and immediate post-intervention.
2. Percentage change in amplitude of motor evoked potential (MEP) to immediate post-intervention. Motor cortical excitability is measured by electromyography using MEPs elicited by TMS Time Frame: Baseline and immediate post-intervention.
3. Change from baseline functional connectivity to PPC stimulation target within the cortical grasping network to immediate post-intervention. Resting-state connectivity of low frequency BOLD fluctuations for a seed at the PPC. Time Frame: Baseline and immediate post-intervention.
4. Change from baseline Blood Oxygen Level-Dependent (BOLD) activation, voxelwise in the cortical grasp network to immediate post-intervention. Parietal-frontal cortical grasping network defined by BOLD change while subject performs the precision force-tracking task. Time Frame: Baseline and immediate post-intervention.

Secondary Outcome Measures:

1. Percentage change in the time to complete the nine-hole peg test (9-HPT) to 1-week post-intervention. 9-hole peg test is a manual dexterity measure, estimated as the time required to complete the task (seconds). Time Frame: Baseline and 7-15 days post-intervention.
2. Percentage change in amplitude of motor evoked potential (MEP) to 1-week post-intervention. Motor cortical excitability is measured by electromyography using MEPs elicited by TMS. Time Frame: Baseline and 7-15 days post-intervention.

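### Primary outcome 3 measures change from baseline at a PPC site chosen as the peak of the baseline imaging, so within-arm change is open to downward selection bias; the vertex arm's seed rule is unstated

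*Combined protocol and SAP*

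**What the plan says.** **Target.** Under rTMS Sessions, the left PPC site is individualised from "peak functional connectivity with the left motor cortex seed obtained at the baseline assessment", and those coordinates become the stimulation site. The scalp position is then refined: "We then will use a robust dual-site TMS 'hunting' procedure". Research Design describes the pre-stimulation assessment for subjects in general, including "fMRI-derived connectivity (providing the PPC target" for iTBS. It schedules one scan before stimulation (session 2). The rTMS Sessions text places this imaging at visit 1, which should be reconciled, but only one pre-stimulation scan is listed.

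**Outcomes.** Primary outcome 3 is "Change from baseline functional connectivity to PPC stimulation target within the cortical grasping network to immediate post-intervention", specified as "Resting-state connectivity of low frequency BOLD fluctuations for a seed at the PPC". Primary outcome 4 is voxelwise change in BOLD activation within a network described as "Parietal-frontal cortical grasping network defined by BOLD change while subject performs the precision force-tracking task".

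**Control arm.** "For the vertex (control) target, we will locate the vertex according to the standard 10-20 system". For this arm, baseline fMRI is mentioned only to confirm that the site lies outside the grasp network.

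**Analysis.** The Aim 3 paragraph under Detailed objectives says "we will directly contrast the MRI sessions following iTBS PPC + Grasp with iTBS PPC alone and iTBS Vertex + Grasp".

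The plan does not state:
- whether rest or task runs set the PPC target;
- whether the analysis seed is the fMRI peak or the TMS-refined site;
- which PPC seed vertex participants receive;
- which session defines the outcome 4 network;
- whether any runs are held out for selection.

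**The concern.** The largest of many noisy measurements is partly large by chance. When the same site is measured again, the chance part is not repeated and the value falls. Outcome 3 takes its starting value at such a maximum, so an inert intervention would appear to lower PPC-M1 connectivity. That is opposite to the strengthening of the pathway that the Aim 1 objective expects.

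Two arms selected in the same way share this fall, and it drops out of their difference. The vertex arm exists to test whether PPC stimulation is specific. If its PPC seed were chosen differently, the PPC-versus-vertex contrast would carry the artefact. Outcome 4 raises a related question, because the task that defines its region also supplies the outcome. Outcomes 3 and 4 are two of the four primary outcomes.

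**Working it through.** **1. The plan's own figure.** The documents give no figure for selection bias. The stated sample size, 54, reproduces as a 3-group by 3-time interaction: f² = 0.11/0.89 = 0.124, df 4 and 102, noncentrality f² × 102 = 12.6, power 0.804. It was sized on behaviour and enters here only as 54/3 = 18 per arm.

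**2. Size of the fall, in SD units.** Assumptions not in the documents: V independent candidate sites, total variance 1 across sites, reliability R, no true change. At the chosen site the expected baseline is E[max of V standard normals] and the expected re-measurement is R times that, so

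expected change = −(1 − R) × E[max].

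| R | V | E[max] | Expected change (SD) |
|---|---|---|---|
| 0.8 | 10 | 1.54 | −0.31 |
| 0.6 | 5 | 1.16 | −0.47 |
| 0.6 | 30 | 2.04 | −0.82 (simulated −0.80) |
| 0.4 | 100 | 2.51 | −1.50 |

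**3. What that means for PPC versus vertex if the vertex seed is not peak-selected.** At R = 0.6 and V = 30, the simulated SD of change is 0.83 with a selected seed and 0.89 with a fixed seed. The SE of the difference is √((0.83² + 0.89²)/18) = 0.287, so the bias is 0.80/0.287 = 2.8 standard errors.

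**4. A second model, in Fisher z.** The 0.009–0.08 Hz filter gives about 2 × 0.071 × 300 = 42.6 effective samples per 5-minute run, with error variance 1/(n − 3). Assumed: 1 to 3 rest runs, 5 to 50 candidate locations, true between-location SD 0.05 to 0.2. Then

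expected change = −[error variance / √(error variance + true variance)] × E[max].

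- Three runs, SD 0.2, 5 locations: error variance 1/(127.8 − 3) = 0.0080, so 0.0080/√0.0480 × 1.16 = 0.04.
- One run, SD 0.05, 50 locations: error variance 1/(42.6 − 3) = 0.0253, so 0.0253/√0.0278 × 2.25 = 0.34.

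The fall is therefore 0.04 to 0.34 z. Simulated two-sided 5% tests with no true effect, 18 per arm, SD 0.1 to 0.2 and 5 to 20 locations, reject as follows.

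| Test of change in outcome 3 | False-positive rate |
|---|---|
| Within a PPC arm | 28% to about 100% |
| PPC + Grasp vs PPC alone | 4.6–5.3% |
| PPC vs vertex, same seed rule | 4.6–5.4% |
| PPC vs vertex, vertex seed fixed and unselected | 16–93% |

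In the last row the spurious difference is −0.04 to −0.25 z.

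**5. Comparing post-stimulation sessions only.** This has no regression from baseline, but it still needs a common seed rule. With unlike rules, the PPC arms are measured at a truly stronger site: R × E[max] = 0.6 × 2.04 = +1.2 SD in the step 3 example. In the second model with three rest runs, false positives were 51% to about 100%. The error now favours PPC stimulation, so its sign depends on which contrast is reported.

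**6. Outcome 4.** Illustration with assumed values: 54 participants, 30% of voxels active, group mask at t > 3.2, no true effect.

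| Mask from | Spurious change | Within-arm rejection | Between-arm rejection |
|---|---|---|---|
| Baseline | −11.5% | 78% | 5.0% |
| Post-intervention | +13.4% | 79% | 4.6% |
| Average of sessions | +0.2% | 5.0% | 4.8% |
| Independent scan | −0.1% | 5.1% | 5.4% |

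**7. Check of the remedy for outcome 3.** Picking the seed on half of the baseline runs and measuring baseline on the other half leaves a spurious change of no more than about 0.001 z.

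**The case against.** The strongest reply is that the plan is already between-arm and that one PPC rule for everyone is its natural reading. The Aim 3 paragraph contrasts arms, and the Aim 3 hypothesis compares PPC + Grasp with PPC alone, where the bias cancels whatever the vertex arm does. Research Design describes the baseline scan as supplying the PPC target without restricting it by arm. The screening session gives subjects in general a parietal-motor dual-site assessment and a trial of iTBS at the PPC target. All of this stands. What remains is that no sentence fixes the seed for the vertex arm in the analysis, and that outcome 3 is defined as change from baseline.

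The size is also open to challenge. Neighbouring voxels are correlated, so the effective number of sites may be small. Selection on task runs, or a seed at the TMS-refined site, would shrink the bias. Connections other than PPC-M1 dilute it. These points stand as limits on the figures. The plan does not adopt any of them as its analysis rule.

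A reader might infer three stronger claims that the documents do not support:
- **That both fMRI primary outcomes are biased.** Outcome 4 names the task but not the session or level of its mask, and the Aim 3 paragraph refers to a network defined in advance. Bias there is possible, not shown.
- **That every between-arm comparison depends on the vertex seed.** PPC + Grasp versus PPC alone does not, and outcome 4 does not use the seed.
- **That vertex participants do get a different seed, or that misleading within-arm results will be published.** The 10-20 rule locates their stimulation site and says nothing about their analysis seed. The plan commits to no within-arm test.

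**Conclusion.** The point holds in a limited form. As written, outcome 3 starts from a value selected for being high, and no held-out runs or fixed seed are planned. If selection and outcome share rest runs and the seed is the fMRI peak, within-arm change in the PPC-M1 connection is biased downward by about 0.3 to 1.5 SD. That range rests on assumed reliability of 0.4 to 0.8 and 10 to 100 independent sites; five effective sites at reliability 0.6 would give about 0.5 SD. The direction is firmer than the size.

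The Aim 3 comparison of the two PPC arms is protected. PPC versus vertex is protected only under a common PPC seed rule, which is plausible but unstated for the analysis. Outcome 4 may be biased within arm, in either direction or not at all, according to the mask session. A mask common to all arms leaves its between-arm contrasts sound. This should be settled in the SAP before the scans are analysed.

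**What to change.** In the Aim 3 analysis:

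1. State one PPC seed rule for all three arms, vertex included, and say whether the seed is the fMRI peak or the TMS-refined site. Base conclusions on outcomes 3 and 4 on between-arm differences adjusted for the baseline value, in place of raw change or a contrast of post-stimulation sessions alone.
2. Report within-arm change in outcome 3 only from a selection-free seed. This can be an atlas or group PPC location fixed without using participants' own baseline peaks, or a seed picked on some baseline runs with baseline measured on the others. The second option needs enough rest data to divide; the plan gives six 5-minute runs but not the rest/task split.
3. Define the outcome 4 mask once for all arms, blind to arm, from an atlas or from the average of all sessions pooled over participants. Baseline data alone should not be used, because that choice gave the −11.5% spurious within-arm change above.

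The cost is some SAP text and a little more analysis, with no new scans or participants. The downside is a less individualised or noisier seed for the within-arm description.

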The objective of Aim 2 is to determine inter-cortical interactions from PPC to motor plasticity. Descriptive statistics will be used to explore the distribution, central tendency, and variation of each measurement. Normality for each variable will be checked using a Shapiro-Wilks test, and appropriate transformations (i.e., log) will be used when necessary. To examine state-dependency modulation of rTMS-induced effects on motor plasticity, we will contrast the size of MEPs elicited in the resting hand muscle by TMS over M1 following iTBS PPC + Grasp with those following iTBS PPC alone. We will test the following: the size of MEPs evoked by TMS will be greater for iTBS PPC alone relative to iTBS Vertex + Grasp, and whether the MEPs will be greater for iTBS PPC + Grasp, compared to iTBS PPC alone. Because the MEP amplitude can be highly variable from trial-to-trial within the same subject,²⁸ we will collect 24 MEPs, the optimal number of single-pulse TMS trials required for the reliable assessment of motor cortical excitability.^{29,30} In addition, to avoid the confounding influence of diurnal variations in levels of cortisol on the induction of cortical plasticity,³¹ all experiments will occur at the same time of day. Based on prior work,³² it is possible that subjects with more excitable motor systems will have greater behavioral improvements after rTMS. We, will therefore perform additional analyses examining the relations of inter-individual differences in MEP amplitude, magnitude of the plasticity effects in the motor system,³³ and the rTMS-induced behavioral effects.³⁴ Knowledge of this variability will provide insight into how interventions can be personalized and optimized for stroke recovery.

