- **Dual-site TMS** will be used to measure functional connectivity in the motor system. The test pulse intensity over the primary motor cortex will be set to produce a MEP of ~ 1 mV at rest. The conditioning pulse intensity will be set between 80% - 120% resting MT. The interstimulus interval will range between 2 – 40 ms. These parameters will be determined based on our previous published work and work by others for each brain site. For PPC brain region, fifteen test pulses and conditioning pulses will be presented randomly at each time interval both at rest or during a task at each time points. Stimuli will be applied every 5 s.

**See below for primary outcome 2, secondary outcomes 2, 11 & 12.*

***(see Appendix for details)*

General assessment procedures with TMS:

- Participants will be required to place their chin on a padded support during the trials to minimize head movement. The support/apparatus level will be placed so that the head is in a natural, upright, comfortable position. To avoid mental and physical fatigue, participants will be allowed breaks between blocks of trials (approximately every 10-15 minutes), where they can lift their head off the chin support or from the apparatus and rest if desired
- Motor-evoked potentials (MEPs) will be elicited by single-pulse TMS stimuli delivered from a MagPro X100 with MagOption Magnetic Stimulator and a 90 mm figure-of-

eight static-cooled coil (MagVenture Inc, Atlanta, GA) and two small figure-of-eight branding-iron coils (inner diameter: 50-70 mm) connected to a Magstim 200² stimulator (Magstim, Whitland, UK).

- MEPs will be recorded from abductor pollicis brevis (APB), first dorsal interosseous (FDI), and abductor digiti minimi (ADM) muscles in both hands with 9 mm diameter Ag-AgCl surface electrodes. The active electrode will be placed over the muscle belly, and the reference electrode over the metacarpophalangeal joint of the finger. The signal will be amplified (1000x), bandpass filtered (20 Hz– 2.5 kHz), digitized at 5 kHz using an amplifier and analog-to-digital interface (Intronix Technologies Model 2024F/ Digitimer D440-4 Low Noise 4-Channel Isolated Amplifier with Micro1401; Cambridge Electronics Design, Cambridge, UK) and stored in a computer for off-line analysis.

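### Aim 2 uses MEP amplitude to mark how excitable a participant is, but amplitude is titrated to about 1 mV in each person and so is a weak marker; motor threshold, already measured, would serve better

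*Combined protocol and SAP*

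**What the plan says.** Aim 2, under Detailed objectives, starts from a supposition: "it is possible that subjects with more excitable motor systems will have greater behavioral improvements after rTMS". To follow it up, the investigators will "perform additional analyses examining the relations of inter-individual differences in MEP amplitude", the size of the plasticity response and the behavioral effects. Plasticity is a separate item in that list, so MEP amplitude stands there as the excitability marker. The paragraph names no time point, model or test for this analysis.

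The Measurements section says that MEP amplitude "will be measured with 1 mV TMS intensity". It adds: "A fixed stimulation intensity to elicit a ~ 1 mV MEP will be determined for each participant before testing". The stated purpose is to follow change after the interventions. The dual-site measure is handled in the same way: "The test pulse intensity over the primary motor cortex will be set to produce a MEP of" about 1 mV at rest. No MEP at a common intensity and no recruitment curve is listed.

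The same section collects motor threshold, "defined as the lowest TMS intensity needed to generate MEPs of" a set size, at rest (RMT) and during contraction (AMT). The Appendix (Motor threshold and MEP amplitude) treats threshold as an index of neuronal excitability. Aim 2 does not name it for this analysis.

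Primary outcome 2 is the percentage change in MEP amplitude from baseline. The inter-individual analysis is additional; it is not among the 4 primary or 12 secondary outcomes.

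**The concern.** Titrating each person to about 1 mV levels out the quantity that the analysis needs to vary. The excitable participant and the less excitable one both start near 1 mV. What distinguishes them is the intensity that each needed, and Aim 2 does not use it.

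Two misreadings could follow. A null relation between amplitude and nine-hole peg test improvement could be taken as evidence against the hypothesis when the marker carried little information. A negative relation with percentage MEP change could be taken to mean that less excitable people respond best, when some or all of it is arithmetic. Aim 2 hopes that this analysis will inform personalized interventions, so both matter for interpretation even though no primary comparison depends on them.

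**Working it through.** **Starting figures.** The plan gives no figure for this analysis. The number of participants, 54, comes from Statistical Design. It can be reproduced with 3 groups, 3 time points, f = √(0.11/0.89) = 0.352 and noncentrality f²(N - 3)(3 - 1), which gives power 0.804. It was derived for action performance and serves here only as the number analyzed. The 24 MEPs per time point come from Measurements. Every variance below is an assumption.

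**Step 1: what titration does.** Write log MEP = E + h(I) + noise, with E the person's excitability and I the intensity. Titration picks I so that E + h(I) = log(1 mV) + c, where c is calibration error. Baseline log amplitude is then log(1 mV) + c + noise, and E has dropped out. A zero correlation with excitability therefore follows from assuming complete titration; it is not an empirical finding.

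**Step 2: loss of information.** Assume a log-scale trial SD of 0.5, calibration on 10 trials and a between-person SD of E of 0.35.

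- Calibration variance: 0.25/10 = 0.0250.
- Variance of a 24-trial mean: 0.25/24 = 0.0104.
- Expected r = true r × √[signal variance/(signal + noise variance)].
- Complete titration: signal variance 0, factor 0.
- One fifth of the spread survives: signal (0.2 × 0.35)² = 0.0049, noise 0.0250 + 0.0104 = 0.0354, factor √(0.0049/0.0403) = 0.35.
- Threshold-type measure (RMT, AMT or the 1 mV intensity): signal 0.35² = 0.1225, noise 0.0250, factor √(0.1225/0.1475) = 0.91.

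Simulation (4000 data sets, two-sided 0.05) agrees with these factors:

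| Marker | Mean r at true r = 0.3 / 0.4 / 0.5 | Power |
|---|---|---|
| Amplitude, complete titration | 0.00 / 0.00 / 0.00 | about 0.05 throughout |
| Amplitude, one fifth survives | 0.10 / 0.14 / 0.17 | 0.11 / 0.18 / 0.24 |
| Threshold-type | 0.27 / 0.36 / 0.45 | 0.50 / 0.79 / 0.95 |

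The smallest correlation detectable with 80% power is tanh[(1.960 + 0.842)/√51] = 0.37 for 54 participants, and tanh[2.802/√15] = 0.62 within one arm of 18. Even a good marker can therefore show only a fairly strong relation.

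**Step 3: baseline against percentage MEP change.** Let T be the titration SD (shared by both sessions), D the session drift SD, S the SD of true between-person change (all on the log scale), and e = 0.0104 the variance of a 24-trial mean. With change unrelated to baseline, on the log scale:

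r = -(D² + e) / √[(T² + D² + e)(2D² + 2e + S²)]

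- T = 0.1, D = 0.3, S = 0: -0.1004/√(0.1104 × 0.2008) = -0.67.
- T = 0.3, D = 0.1, S = 0: -0.0204/√(0.1104 × 0.0408) = -0.30.
- T = 0.3, D = 0, S = 0.5: -0.0104/√(0.1004 × 0.2708) = -0.06.

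Simulated percentage change at n = 54 runs slightly closer to zero, from about -0.6 to about -0.05. The share of data sets significant at 0.05 was:

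- 58% to 100% with no true change and D and T each 0.1 to 0.3;
- about 6% to 99% with S of 0.3 to 0.5 and D of 0 to 0.3.

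Within one arm of 18, the latter settings gave about 5% to 62%. Mean r was negative in every setting, including on the log scale.

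**The case against.** **Baseline is an inference.** Earlier in the same paragraph the MEPs contrasted are those recorded after iTBS, and Measurements says that the fixed intensity serves "MEP will be determined for each participant before testing to examine the changes in MEP after the different plasticity induction protocols". Relating that response to behavior would be a sound use of a titrated measure. This stands as a point about wording. It does not rescue the analysis, because a post-iTBS MEP measures response, whereas the hypothesis concerns excitability that was there beforehand.

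**Some signal may remain.** The 1 mV target is approximate, and MEPs are recorded from three muscles in both hands, which one intensity cannot all bring to 1 mV. A reader might infer that baseline amplitude can carry no information on excitability; the documents do not support that. The one-fifth row of the table shows how weak a partial signal would be.

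**The spurious correlation is neither certain nor prescribed.** A reader might infer that the analysis will usually produce a false positive. That needs little or no true variation in response, whereas Aim 2 expects people to differ. Nor does the plan explicitly commit to testing baseline amplitude against percentage change; it speaks only of relations among three quantities. Both points stand. Only the negative direction is common to all settings. The log transformation that Aim 2 allows does not remove it.

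**The stakes are limited.** This is an additional analysis with no alpha or power of its own, and no data are lost. That also stands.

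**Conclusion.** The concern holds as a mismatch between a hypothesis about excitability and a marker designed to follow change. On the natural reading, titrated baseline amplitude is a weak and largely uninformative predictor. How weak depends on how much spread survives titration: power of about 5% to 24% against 95% for a threshold-type measure, at a true correlation of 0.5 and with the assumed variances.

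The second problem is conditional. If baseline amplitude is related to percentage MEP change, the correlation is biased downward by an amount that the documents cannot fix.

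A reader might go further and doubt primary outcome 2. The documents give no ground for that here: a fixed intensity near 1 mV suits a change score. The point deserves a correction to the analysis text and affects no primary comparison.

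**What to change.** In the Aim 2 inter-individual analysis, name RMT, or the stimulator output that gives about 1 mV, as the excitability marker, recorded before rTMS, with AMT as a sensitivity analysis. Note the sign: a higher threshold or output means lower excitability. The Appendix says that threshold and MEP amplitude both also reflect subcortical and spinal excitability, so the marker should be described as corticospinal.

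Add that a raw correlation of baseline MEP amplitude with percentage MEP change will not be interpreted.

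The cost is one or two sentences. Thresholds and the 1 mV intensity are already determined under the plan, so no new data, visits or changes to participant procedures are needed; the 1 mV output has only to be kept in the data set.
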